6.2 Study populations

Safety population

A safety population will be defined separately for, maternal participants and their infant participants. For the safety analyses, maternal participants will be analysed according to the investigational product received and infant participants will be analysed according to the investigational product their mothers (maternal participants) received.

- Maternal participants: All maternal participants receiving a dose of GBS6 or placebo will be included in the safety population.
- Infant participants: All infant participants who are enrolled in the study will be included in the safety population.

Immunogenicity population

Two populations will be defined separately for maternal participants and their infant participants: evaluable immunogenicity population and modified intent-to-treat (mITT) populations. Immunogenicity data will be analysed separately for maternal participants and their infant participants.

For the immunogenicity analyses, maternal participants will be analysed according to the investigational product received for the evaluable immunogenicity population and the investigational product as randomised for the mITT population. Infant participants will be analysed according to the investigational product received by their mothers (maternal participants) for the evaluable immunogenicity population and the investigational product assigned to

A placebo controlled clinical trial investigating the safety and immunogenicity of GBS6 in pregnant women with and without human immunodeficiency virus (HIV) infection and their infants

Protocol Version 5.0, Dated 01/02/2023

Protocol Version/date 5.0,01/02/2023
R&D Protocol Code Number:
Page:32

their mothers (maternal participants) for the mITT population. The evaluable immunogenicity population is considered to be the primary population for the immunogenicity analyses.

- Maternal participants

To be included in the evaluable immunogenicity population, the maternal participant must have been eligible for the study, have received GBS6 or placebo as randomised, have had blood drawn within the specified time frames, have at least one valid and determinate assay result for the proposed analysis, and have no other major protocol violations. To be included in the mITT population, the maternal participant must be randomised and have at least one valid and determinate assay result related to the proposed analysis.

- Infant participants

To be included in the evaluable immunogenicity population, the infant participant must have been eligible for the study, the infant participant's mother must have received GBS6 or placebo as randomised, and the infant participant must have had blood drawn within the specified time frames, have at least one valid and determinate assay result for the proposed analysis, and have no other major protocol violations. To be included in the mITT population, the infant participant's mother must be randomised and the infant participant must have at least one valid and determinate assay result related to the proposed analysis.

6.3 Statistical methods

Safety data will be analysed separately for maternal participants and their infant participants.

- Descriptive analysis

A flowchart will be used to summarise the number of mothers approached, consented, recruited, assigned to the different study arms, receiving the intended vaccines, completing the study protocol and analysed for the primary outcome, as recommended by the CONSORT statement (<http://www.consort-statement.org/>).

- Statistical significance and confidence intervals

A placebo controlled clinical trial investigating the safety and immunogenicity of GBS6 in pregnant women with and without human immunodeficiency virus (HIV) infection and their infants

Protocol Version 5.0, Dated 01/02/2023

Protocol Version/date 5.0,01/02/2023
R&D Protocol Code Number:
Page:33

MAKERERE UNIVERSITY
SCHOOL OF MEDICINE
APPROVED AMENDMENT
Valid Until

★ 30 NOV 2023 ★

RESEARCH & ETHICS COMMITTEE
[name]

5% significance will be used and 95% confidence intervals.

- Statistical software

Statistical analyses will be performed on STATA version 15 or similar.

- Missing data

Analysis will be by modified intention to treat (mITT), meaning individuals are analysed according to the group they are randomised to, but only those with at least one blood taken and antibody result will be included, with missing data (e.g. from withdrawals, non-compliers) assumed missing at random. Missing data will be excluded from relevant analyses. The mITT analysis will include blood samples taken outside the recommended timing. A per-protocol analysis will also be performed if there are major protocol deviations. Spurious data will be checked to source records and investigated but included if no cause is identified.

- Outliers, censored data and non-normal data

Outliers will be included in the analyses and investigated assuming no errors have occurred. We will assign all results of <2 a value of 1 for calculation of geometric means. Antibody concentrations will be log-transformed for analyses of mean antibody levels.

- Statistical analysis for each objective and outcome

Statistical Analysis of primary endpoints

The followings are the primary analyses for each of the outcomes related to primary objectives.

- Maternal primary endpoint 1:

Proportion of maternal participants reporting solicited local reactions within 7 days following administration of GBS6 vaccine will be calculated with exact binomial 95% confidence

A placebo controlled clinical trial investigating the safety and immunogenicity of GBS6 in pregnant women with and without human immunodeficiency virus (HIV) infection and their infants

Protocol Version 5.0, Dated 01/02/2023

Protocol Version/date 5.0,01/02/2023
R&D Protocol Code Number:
Page:34

intervals for each group. Comparison between groups (GBS v Placebo within each HIV strata) will be by Fisher's exact test.

- Maternal primary endpoint 2:

Proportion of maternal participants reporting solicited systemic events within 7 days following administration of GBS6 vaccine will be calculated with exact binomial 95% confidence intervals for each group. Comparison between groups (GBS v Placebo within each HIV strata) will be by Fisher's exact test.

- Maternal primary endpoint 3:

Proportions of maternal participants reporting solicited and unsolicited adverse events through 1 month following administration of GBS6 vaccine will be calculated with exact binomial 95% confidence intervals for each group. Comparison between groups (GBS v Placebo within each HIV strata) will be by Fisher's exact test.

- Maternal primary endpoint 4:

Proportions of maternal participants with SAEs, MAEs, and obstetric complications (peripartum, intrapartum, and postpartum) throughout the study (Visit 1 through the 12-month postdelivery study visit) and any unsolicited events leading to study withdrawal following administration of GBS6 vaccine will be calculated with exact binomial 95% confidence intervals for each group. Comparison between groups (GBS v Placebo within each HIV strata) will be by Fisher's exact test.

- Infant primary endpoint 1:

Proportions of infants with unsolicited adverse events from birth to 6 weeks of age month following administration of GBS6 vaccine will be calculated with exact binomial 95% confidence intervals for each group. Comparison between groups (GBS v Placebo within each HIV strata) will be by Fisher's exact test.

A placebo controlled clinical trial investigating the safety and immunogenicity of GBS6 in pregnant women with and without human immunodeficiency virus (HIV) infection and their infants

Protocol Version 5.0, Dated 01/02/2023

Protocol Version/date 5.0,01/02/2023
R&D Protocol Code Number:
Page:35

- Infant primary endpoint 2:

Proportions of infants with SAEs, AEs of special interest (major congenital anomalies, developmental delay, and suspected or confirmed GBS infection), and MAEs through 12 months of age and any unsolicited events leading to study withdrawal following administration of GBS6 vaccine will be calculated with exact binomial 95% confidence intervals for each group. Comparison between groups (GBS v Placebo within each HIV strata) will be by Fisher's exact test.

Statistical analysis of secondary endpoints

The followings are the primary analyses for each of the outcomes related to secondary objectives.

- Maternal secondary endpoint 1:

Antibody levels for GBS serotype-specific antibody concentrations measured at baseline, 2 weeks, 1 month after vaccination, at delivery, and 6 weeks after delivery in HIV positive and HIV negative women will be described using box-and-whisker plots with a log-scale y-axis. GMTs of GBS serotype specific antibody concentrations measured at baseline, 2 weeks, 1 month after vaccination, at delivery, and 6 weeks after delivery in HIV positive and HIV negative women will be calculated with 95% confidence intervals post vaccinations and the groups will be compared using unpaired t-tests or the Kruskal Wallis test if log-titres are not normally distributed.

Reverse cumulative distribution curves (RCDCs) of antibody concentrations by vaccine groups will be generated for each GBS6 serotype. Additionally, graphs of geometric means and the associated 95% CIs of the antibody concentrations will be presented at each analysis time point by vaccine group and serotype. The proportions of participants achieving defined GBS6 serotype specific IgG concentrations will be summarised descriptively at prespecified time points as counts and percentages with 2-sided 95% exact CIs by vaccine group and HIV

A placebo controlled clinical trial investigating the safety and immunogenicity of GBS6 in pregnant women with and without human immunodeficiency virus (HIV) infection and their infants

Protocol Version 5.0, Dated 01/02/2023

Protocol Version/date 5.0,01/02/2023
R&D Protocol Code Number:
Page:36

MAKERERE UNIVERSITY
SCHOOL OF MEDICINE
APPROVED AMENDMENT
Valid Until

★ 30 NOV 2023 ★

RESEARCH & ETHICS COMMITTEE
[name]

status. Groups 1 vs 2, 3 v 4 will be compared by a t-test or Kuskal-Wallis test if logged data are not normally distributed.

- Maternal secondary endpoint 2:

For each serotype, GBS serotype specific IgG GMT measured at baseline, and at delivery in HIV positive and HIV negative women will be calculated for each group with 95% confidence intervals. Groups 1 vs 2, 3 v 4 will be compared using similar methods to those for IgG concentrations.

- Infant secondary endpoint 1:

GMCs of GBS serotype specific IgG concentrations in HIV-exposed and unexposed infant participants measured at birth, 18 weeks and 12 months of life will be calculated at all blood draw visits for each group with 95% confidence intervals. Groups 1 vs 2, 3 v 4 will be compared using similar methods to those for maternal IgG concentrations.

- Infant secondary endpoint 2:

GMTs of GBS serotype specific IgG GMT in HIV-exposed and unexposed infant participants measured at 18 weeks of life will be calculated for each group with 95% confidence intervals. Groups 1 vs 2, 3 v 4 will be compared

- Infant secondary endpoint 3:

For each serotype, placental transfer ratio (infant GMC in cord blood or infant blood collected within 72 h of birth divided by maternal GMC in blood collected at delivery) will be calculated for each group with 95% confidence intervals. Groups 1 vs 2, 3 v 4 will be compared using similar methods to those for IgG concentrations.

Statistical analysis of exploratory endpoints

A placebo controlled clinical trial investigating the safety and immunogenicity of GBS6 in pregnant women with and without human immunodeficiency virus (HIV) infection and their infants

Protocol Version 5.0, Dated 01/02/2023

Protocol Version/date 5.0,01/02/2023
R&D Protocol Code Number:
Page:37

The followings are the primary analyses for each of the outcomes related to exploratory objectives.

- Maternal exploratory endpoint 1: The geometric mean fold ratio with a two-sided 95% CI will be calculated for group 4/group2. To account for differences between HIV positive and negative mothers the ratio of group 4/group 2 will be adjusted in a normal errors regression model on logged titers with terms included for covariates including maternal age, gestation and birth weight.

Maternal exploratory endpoint 2: Proportions of maternal participants with GBS colonisation assessed by vaginal and rectal swab before vaccination, at delivery, and 6 weeks after delivery will be calculated with exact binomial 95% confidence intervals for each group.

Comparison between groups (GBS v Placebo within each HIV strata) will be by Fisher's exact test.

- Maternal exploratory endpoint 3: For each serotype, IgA/IgG GMCs will be calculated at all breast milk visits for each group with 95% confidence intervals. Groups 1 vs 2, 3 v 4 will be compared using similar methods to those for blood IgG concentrations.

- Infant exploratory endpoint 1: The proportion of infant participants achieving defined levels of IgG to diphtheria toxoid and 13-valent pneumococcal conjugate vaccine serotypes will be summarised descriptively at 18 weeks and 12 months of age. Groups 1 vs 2, 3 v 4 will be compared using similar methods to those for GBS IgG concentrations.

- Infant exploratory endpoint 2: Proportions of infant participants with GBS colonisation assessed by nasal/rectal swabs at birth and at 6 weeks and 18 weeks of age will be calculated with exact binomial 95% confidence intervals for each group. Comparison between groups (GBS v Placebo within each HIV strata) will be by Fisher's exact test.

- Infant exploratory endpoint 3: For each serotype, GMCs will be calculated from dried blood spots in infant participants at births for each group with 95% confidence intervals.

A placebo controlled clinical trial investigating the safety and immunogenicity of GBS6 in pregnant women with and without human immunodeficiency virus (HIV) infection and their infants

Protocol Version 5.0, Dated 01/02/2023

Protocol Version/date 5.0,01/02/2023
R&D Protocol Code Number:
Page:38

Note that detailed analyses of all the endpoints including additional exploratory analyses and graphical displays will be described in the SAP.

A placebo controlled clinical trial investigating the safety and immunogenicity of GBS6 in pregnant women with and without human immunodeficiency virus (HIV) infection and their infants

Protocol Version 5.0, Dated 01/02/2023

Protocol Version/date 5.0,01/02/2023
R&D Protocol Code Number:
Page:39

7. Trial design

This is a randomised, placebo controlled, double-blind, parallel group study which will be based at Kawempe Specialised National Referral Hospital, Kawaala and Komamboga Health Centre III and Wakiso and Kisenyi Health Centre IV, Uganda.

Subjects will be a randomized 1:1 to GBS6/placebo stratified by baseline HIV status:

1. HIV-uninfected women, placebo (saline) in pregnancy;
2. HIV-uninfected women, GBS6 in pregnancy;
3. HIV-infected women, placebo (saline) in pregnancy;
4. HIV-infected women, GBS6 in pregnancy;

	HIV-uninfected pregnant woman	HIV-infected pregnant woman
Placebo (saline) in pregnancy	Group 1 (n=75)	Group 3 (n=75)
GBS6 in pregnancy	Group 2 (n=75)	Group 4 (n=75)

A placebo controlled clinical trial investigating the safety and immunogenicity of GBS6 in pregnant women with and without human immunodeficiency virus (HIV) infection and their infants

Protocol Version 5.0, Dated 01/02/2023

Protocol Version/date 5.0,01/02/2023
R&D Protocol Code Number:
Page:40

8. Participant Selection criteria

There will be no exceptions (waivers) to eligibility criteria prior to participant inclusion into the study. Any questions raised about eligibility should be addressed prior to enrolling the participant.

The eligibility criteria have been carefully considered and are standards used to ensure the trial results can be appropriately used to make future treatment decisions for other people with similar disease or medical condition. It is therefore vital that exceptions are not made to the following detailed selection criteria.

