4.7. Developing a sero-correlate of protection against GBS

Although maternal GBS colonisation is common, very few colonised infants (1-2%) subsequently develop invasive GBS disease ²⁶. Studies indicate that high concentrations of naturally occurring capsular serotype-specific maternal IgG antibody correlate with a reduced risk of disease in neonates ²⁵. The association between serotype-specific capsular polysaccharide (CPS) antibody levels and GBS in newborns was initially characterised in 1976 by Baker and colleagues ²⁷. In all subsequent studies lower serotype-specific CPS antibodies were found in infants with early onset (EO) and late onset (LO) GBS compared with controls. In a meta-analysis comparing the proportions of cases and controls with CPS antibody levels ≥ 2 ug/ml, the odds of GBS was 6.56 (95% CI: 2.10–20.55) and 2.38 (95% CI: 1.20–4.70) times greater in infants whose mothers had antibody levels < 2 ug/ml for serotypes III and Ia, respectively ²⁸. A threshold of 1 ug/ml has also recently been proposed as a correlate for protection for serotypes Ia and III ²⁹. Thresholds are much higher in other large studies ³⁰ including a study from South Africa ³¹. Interpretation of these studies is difficult due to differences in endpoints (EO vs LO), assays and statistical analyses, as well as the lack of reference sera.

A placebo controlled clinical trial investigating the safety and immunogenicity of GBS6 in pregnant women with and without human immunodeficiency virus (HIV) infection and their infants

Protocol Version 5.0, Dated 01/02/2023

Protocol Version/date 5.0,01/02/2023
R&D Protocol Code Number:
Page:25

MAKERERE UNIVERSITY
SCHOOL OF MEDICINE
APPROVED AMENDMENT
Valid Until

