6.1 Sample size

This is a Phase 2 randomised, placebo controlled, double-blinded study to assess safety, tolerability, and immunogenicity of GBS6 in pregnant HIV positive and HIV negative women and their infant participants. It will be the first evaluation of the investigational GBS6 vaccine in HIV-infected pregnant women. This study will enroll pregnant women with and without HIV to receive the GBS6 in order to provide an expanded safety and immunogenicity data set (for both pregnant women and their infants) and to support progression of the development of this vaccine. As such, the statistical analyses are largely descriptive and the sample size is chosen based on what is achievable at the site. Additionally, and consistent with the clinical phase of the study (II), the primary outcome is based on safety.

Regarding safety, for common pregnancy outcomes such as prematurity, this sample size of 300 in total would provide 80% power (5% alpha) to detect an increase in prematurity outcomes from a background rate of 10% in the placebo arm, to at least 22% in the vaccine arm.

For the secondary objectives of immunogenicity, approximately 300 pregnant women will be enrolled in this study, 150 participants at the selected GBS6 dose/formulation (75 HIV positive and 75 HIV negative) and 150 participants in the placebo group (75 HIV positive and 75 HIV negative). Based on data from a recent study (20), the standard deviation (SD) of the GMT responses to serotypes Ia, Ib and III is expected to be around 2.55 log e units.

With 75 women per group, the study will have at least 80% power (5% alpha) to detect at least 3.24-fold higher antibody responses post-vaccination in vaccinated participants compared with placebo.

A placebo controlled clinical trial investigating the safety and immunogenicity of GBS6 in pregnant women with and without human immunodeficiency virus (HIV) infection and their infants

Protocol Version 5.0, Dated 01/02/2023

Protocol Version/date 5.0,01/02/2023
R&D Protocol Code Number:
Page:31

	HIV-uninfected pregnant women	HIV-infected pregnant women
Placebo	Group 1 (n=75)	Group 3 (n=75)
GBS6 vaccine	Group 2 (n=75)	Group 4 (n=75)

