12.3. GBS antibody testing

Sera collected from maternal participants throughout the study and from infant participants will be assayed for GBS6 serotype specific anti-capsular antibodies. Sample collection, processing, storage, and shipping information can be found in the study SOP or equivalent manual. OPA results will be reported as OPA titers. Concentrations of anti-capsular IgG for the 6 serotypes (Ia, Ib, II, III, IV, and V) will be determined in all participants for each blood sample by direct Luminex immunoassay (dLIA) and reported as IgG concentrations. Concentrations of anti-capsular IgG for the 6 serotypes (Ia, Ib, II, III, IV, and V) may be determined in samples eluted from dried blood spots taken at birth from infant participants as part of exploratory analyses. In addition, other isotypes and subtypes may be measured for exploratory analyses.

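### The rule setting every result below 2 to 1 for geometric means names no unit or assay; taken literally it overwrites measured values in any assay that quantifies below 2.

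*Protocol*

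**What the plan says.** The rule stands in protocol section 6.3, under the item on outliers, censored data and non-normal data: "We will assign all results of <2 a value of 1 for calculation of geometric means". The sentence after it sends antibody concentrations to a log-scale analysis. No exception is made by assay, serotype, sample type or unit.

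The measurements it governs are not on one scale. Section 12.3 has anti-capsular IgG measured "by direct Luminex immunoassay (dLIA) and reported as IgG concentrations", without a unit, while "OPA results will be reported as OPA titers". Section 6.3 plans geometric means for maternal and infant serum IgG, the placental transfer ratio built from them, breast-milk IgA and IgG, and infant dried blood spots. The first maternal exploratory endpoint is a fold increase over baseline.

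The only concentration unit given anywhere for GBS antibody is ug/ml, in the background section 4.7, which discusses thresholds of 2 ug/ml and 1 ug/ml from other studies ("A threshold of 1 ug/ml has also recently been proposed as a correlate for protection").

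Section 6.1 supplies the spread: "the standard deviation (SD) of the GMT responses to serotypes Ia, Ib and III is expected to be around 2.55 log e units". For the design effect, it claims that groups of 75 give 80% power or more "to detect at least 3.24-fold higher antibody responses post-vaccination in vaccinated participants compared with placebo".

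**The concern.** A cut-off of 2 replaced by 1 is sensible where 2 is the lowest result the assay can report. It does harm where the assay quantifies below 2. Results of 0.05, 0.9, 1.1 and 1.9 would then all enter the geometric mean as 1, although they differ and were measured. One bare number cannot be the right limit for concentrations and titres, or for serum, milk and blood spots, unless their limits happen to coincide.

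The estimates at stake are geometric means and their ratios: vaccine against placebo within each HIV stratum, rise over baseline, and infant over maternal concentration at birth. A transfer ratio moved towards 1 matters here because section 4.4 gives reduced placental transfer in HIV-exposed infants as a motivating question.

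Details may be left to the SAP, but this number is fixed in the protocol, so an SAP that follows the protocol inherits it.

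**Working it through.** **Inputs from the protocol.** SD 2.55 log e units, 75 per group, 5% alpha (taken as two-sided), design ratio 3.24 (section 6.1); cut-off 2 and replacement value 1 (section 6.3).

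**Assumptions.** Results are log-normal and can be measured below 2 in the reporting unit, as they could be in ug/ml. The placebo GMC is not given, so a range is shown.

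**The protocol's own figure.** SE of a difference in log means = 2.55 × √(2/75) = 0.416. ln 3.24 = 1.176, and 1.176/0.416 = 2.82. Power = Φ(2.82 − 1.96) = 80.6%, which agrees with the stated 80% or more. That calculation ignores the cut-off.

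**Effect of the rule.** Let X = ln(result) be normal with mean μ and SD σ. The rule analyses Y = 0 if X < ln 2, and Y = X otherwise. With a = (ln 2 − μ)/σ:

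- share replaced = Φ(a)
- E[Y] = μ(1 − Φ(a)) + σφ(a)
- E[Y²] = (μ² + σ²)(1 − Φ(a)) + σ(2μ + σa)φ(a)

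*Worked case: placebo GMC 0.5, vaccine GMC 0.5 × 3.24 = 1.62.*

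- Placebo: a = 0.544, Φ = 0.707, φ = 0.344. E[Y] = −0.693 × 0.293 + 2.55 × 0.344 = 0.674, so the reported GMC is 1.96.
- Vaccine: a = 0.083, Φ = 0.533, φ = 0.398. E[Y] = 0.482 × 0.467 + 2.55 × 0.398 = 1.239, so the reported GMC is 3.45.
- Reported ratio = exp(1.239 − 0.674) = 1.76.
- SDs of Y are 1.26 and 1.67, so SE = √((1.26² + 1.67²)/75) = 0.242. Power = Φ(0.565/0.242 − 1.96) = 65%.

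The same steps over the range, SD 2.55, true ratio 3.24:

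| Assumed placebo GMC | Below 2: placebo / vaccine | Reported ratio | Power |
|---|---|---|---|
| 0.1 | 88% / 76% | 1.33 | 46% |
| 0.5 | 71% / 53% | 1.76 | 65% |
| 1 | 61% / 42% | 2.00 | 70% |
| 2 | 50% / 32% | 2.26 | 74% |
| 10 | 26% / 14% | 2.81 | 79% |
| 100 | 6% / 2% | 3.18 | 80% |

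**Larger true effects, SD 2.55.** GMC 0.1 against 5, truly 50-fold, is reported as 5.8. GMC 0.5 against 5, truly 10-fold, is reported as 3.7. For a true 20-fold ratio at placebo GMC 0.1, 0.5 and 1, the reported ratios are 3.10, 6.39 and 8.52, with power still about 100%.

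**Placental transfer, true ratio 0.60.** Maternal GMC 5 gives E[Y] = 1.984; infant GMC 3 gives 1.623. Reported ratio = exp(1.623 − 1.984) = 0.70 (0.65 at SD 1.5).

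**Sensitivity to the SD.** At SD 1.5 the design ratio becomes 1.14, 1.72, 2.15 and 3.20 at placebo GMC 0.1, 0.5, 1 and 10. At SD 1.0 and placebo GMC 5 it becomes 3.31, slightly above the truth, because there the main effect is to lower values between 1 and 2.

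**With half an assay-specific limit.** The limit is not in the protocol. At SD 2.55 and an assumed limit of 0.01, placebo GMC 0.1, 0.5 and 1 give ratios 2.97, 3.18 and 3.21 and power 79.7%, 80.5% and 80.6%. At a limit of 0.1 and placebo GMC 0.1, half of the placebo results are still below the limit; the ratio is 2.26 and power 74%.

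**The case against.** The strongest reply is that the sentence is a normal limit-of-detection convention. It sits under a heading that mentions censored data, a laboratory may report a low result simply as <2, and 1 is exactly half of 2. Read that way, no measured value is lost. This is a plausible intention, and it stands as a reason not to treat the sentence as a deliberate flooring of data. It does not save the wording, which covers all results and names neither an assay nor a limit.

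A reader might go further and infer that the trial will under-report the vaccine effect. The documents do not support that. Sections 12.2 and 12.3 give no unit for the IgG assay; the ug/ml figures in section 4.7 come from other studies, and that section itself warns that assays differ. No placebo or post-vaccination GMC is given. Nor is the direction universal, as the SD 1.0 case shows. It would also be too strong to say that low groups are reported at about 1: at SD 2.55 a true 0.5 is reported as 1.96.

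The scope has limits too. The rule applies only to geometric means. Reverse cumulative distribution curves and proportions reaching a defined concentration are outside it, as is the planned proportion-based summary of infant diphtheria and pneumococcal IgG. Immunogenicity is secondary and mostly descriptive, and for large true effects the size of the estimate suffers but not its significance. For transfer from vaccinated women, which is the stated objective, the distortion at GMC 5 is from 0.60 to 0.65–0.70, not the near-total loss seen at very low concentrations.

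**Conclusion.** The concern holds as a defect in a stated rule. A single unit-free cut-off is applied to every geometric mean although the assays and sample types differ, and followed literally it overwrites measured values wherever an assay quantifies below 2.

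The consequence is conditional. If IgG is reported in ug/ml and many values are below 2, ratios, fold rises and transfer ratios are generally pulled towards 1. At the protocol's SD the 3.24-fold design ratio would be reported as roughly 1.3 to 2.8 for placebo GMCs from 0.1 to 10, and power for it would be 46% to 79%. These figures rest on the assumed unit, the assumed GMCs and log-normality. If almost no results fall below 2, nothing changes. The stated power calculation itself reproduces; it simply does not allow for this rule. The sentence should be corrected, but there is no basis for saying that the results will be biased.

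**What to change.** Replace the sentence in section 6.3 with:

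> Results below the lower limit of quantification of the given assay, serotype and sample type are set to half that limit for geometric means; results at or above the limit are used as measured.

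State the reporting unit of the IgG assay in section 12.3, and keep the replacement of <2 by 1 only for an assay whose lower limit is 2. The limits themselves can be listed in the SAP.

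A censored (Tobit) regression as a sensitivity analysis is optional. It would be most useful if many results fall below the limit, since half-limit substitution also compresses ratios then. If it is added, fix the share below the limit that triggers it in advance.

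The cost is a wording change and a request to the laboratory for its limits. It needs no new data and no change to the sample size, and is best settled before unblinding.
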